Planned enrolment	3 municipalities and 9 municipality districts

Sample size estimation

The required sample size calculated before recruitment of participants aimed to detect a difference of 7 h/week for the primary outcome RUD. Based on the literature[4], we assumed that the number of hours of informal care is 46 h/week with a standard deviation (SD) of 20 h/week. With 80% power and a significance level of 5%, the required sample size was estimated to be 260 dyads. To allow for 20% loss to follow-up, a total of 315 dyads, equaling 105 per municipality, must be included.

The post-hoc sample size calculations based on the outcome PADL showed that by treating the study as an individually randomized stepped wedge design[3], with 3 intervention sequences, 5 periods, effect size of 7h/week, outcome variance of 400, significance level of 5% and within-individual correlation of 0.1075 over the 24 month trial would require a total of 240 dyads to be included. To allow for 20% loss to follow-up, the sample size must reach 288 dyads.

Randomization, blinding and unblinding procedures

Block randomization was performed using a computerized random number generator to allocate individual dyads to the three intervention sequences. We will apply stratification to secure that about one third of the dyads in each treatment sequence will be recruited from each municipality. Research assistants, researchers conducting the analyses and other study personal conducting data collection will be blinded to the randomization order, the dyads will be blinded to group allocation until contacted by their coordinator at start of the intervention period. Given the practice change of the intervention, the municipality home care services and coordinators will be informed about allocation sequence when their clusters entered the intervention period.

Analysis Sets

Full Analysis Set (FAS)

The intention-to-treat population includes all randomized dyads who were assigned a coordinator by the municipality. The dyads will be analyzed separately (i.e., PwD and caregiver), dependent on outcome of interest.

This will be the primary analysis set for baseline summary statistics of demographics, primary, secondary and exploratory efficacy analysis as elaborated in section 10.

Municipal coordinator set (MCS)

All coordinators in all municipality districts

Usage overview of analysis sets table

Analyses	FAS	MCS	
Disposition			
Demographics and background	x		
Medical history			

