- Formal caregiver (whether dyads are receiving care by home nursing)
- Categories of caregiver burden intensity
- Categories of dementia diagnoses

Results from subgroups will be presented for the primary analyses.

Observation and analysis times

Study periods

Timeline															
Groups/participants	Inclusion period	Control group			Kristiansand 3, N=35			Bærum 3, N=35			Bergen 3, N=35				
					Kristiansand 2, N=35										
					Bærum 2, N=35										
					Bergen 2, N=35										
		Kristiansand 1, N=35						Follow up							
Number of months		0	1 2	3 4	5 6	7 8	9 10	11 12	13 14	15 16	17 18	19 20	21 22	23 24	
Date		01.09 2019		01.03 2020		01.09 2020		01.03 2021							

		STUDY PERIOD							
		Enrollment		Allocation	Post-allocation				Close-out
TIMEPOINT	-t	0		t1	t2	t3	t4	t5	
ENROLLMENT:									
Eligibilityscreen	x								
Informed consent	x								
Allocation		x							
INTERVENTIONS:									
1st group			x	x					
2nd group				x	x				
3rd group					x	x			
ASSESSMENTS:									
Baseline variables			x						
Outcome variables				x	x	x	x	x	

The stepped wedge randomized control design. A) The randomization in time takes place at month 0. First group (red) is in the intervention period from month 1 to 6, second group (yellow) from month 7 to 12, third group (green) from month 13 to 18. Implementation seminars will be held at month 0, 6 and 12, midway evaluation at month 3, 9 and 15. Data will be collected at baseline (month 0), after first intervention period (month 6-7), after second intervention period (month 12-13), after third intervention period (month 18-19) and at end of study at 24 months. B) Schedule of enrollment, interventions and assessments over the study period.

Demographics and Background Characteristics

Demographics and baseline characteristics

The following demographic characteristics will be presented descriptively and listed for both PwD and caregiver:

- Sex (male, female)
- Age in years
- Marital status (spouse, child)
- Work status (employed, unemployed, retired)
- Number of co-caregivers
- MMSE total score
- RUD (number of care hours the last 30 days)
- RSS total score
- NPI total score
- QoL total score

Date of informed consent and protocol version will be listed

Medical history

We will provide information on the number of years since formal diagnosis of dementia together with descriptive statistics.

Exposure and Compliance

Treatment groups

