The definition of treatment assignment as specified in section “Analysis sets” will be used in this section, too.

Deviations from the randomized treatment sequence occurred under the first Covid-19 lockdown, see section Modification History, Changes to the study protocol

Treatment duration

Each municipal coordinators are writing logs, and we will collect the data and calculate total hours of care by the coordinator, divided into different categories.

Descriptive statistics for the total hours of care by the coordinators will be presented.

Delivery of the intervention

One coordinator from the municipal per dyad

Efficacy

Primary efficacy analysis

The primary efficacy analysis variable caregiver burden is based on two variables. The first is RUD, divided in three categories: number of hours the last 30 days invested in personal, instrumental and supervisory care. The second is RSS measured as total score but also

specific and clustered items. Lower hours of informal care as well as lower score of RSS, indicates reduction in caregiver burden.

The null hypothesis states that there are no differences in burden and resource utilization between the LIVE intervention and usual care. The primary alternative hypothesis (H1) states that the LIVE intervention will improve caregiver burden and resource utilization compared with usual care. The secondary alternative hypothesis (H2) is that the LIVE intervention will provide more cost-efficient services than usual care.

H0: LIVE treatment = control

H1: LIVE treatment > control

H2: cost efficiency > control

where LIVE treatment denotes the proportion of caregivers experiencing improvement in care burden. The primary hypothesis will be statistically assessed by means of a χ^2 test on the one-sided significance level of 2.5% (corresponding to 5% two-sided).

We will plot the regression line to visualize the parallel effect for both treatment group and control group.

The significance level will be set to 2.5% (one-sided, corresponding to 5% two-sided), the corresponding level of one-sided CI is 97.5% (corresponding to 95% two-sided).

Missing data

We will pre-specify a list of baseline covariates that are likely associated with the missingness and the outcome, and adjust for these covariates in our primary analyses. This covariate-adjusted analysis will be valid under the missing at random (MAR) mechanism.

Sensitivity and robustness tests of regression analyses and economic evaluation

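### Burden subgroups are formed on the primary outcome with no instrument, cut-point or time of classification, and model (1) has no period term, so regression to the mean can appear as a LIVE effect

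*SAP*

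**What the plan says.** In the SAP, Covariates and strata, the Subgroups list includes "Categories of caregiver burden intensity", and the section closes with "Results from subgroups will be presented for the primary analyses". Under Efficacy, Primary efficacy analysis, "The primary efficacy analysis variable caregiver burden is based on two variables": RUD hours in three categories, and RSS. The subgroup factor and the outcome are therefore the same construct. Nothing states which instrument forms the categories, where the cuts lie, or at which visit a caregiver is classified.

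The Causal model section writes model (1) with an intercept, a treatment indicator O, covariates X and a random intercept per participant. The text says that time-related confounding matters in a closed cohort. Yet the equation has no period term, and the listed contents of X (demographic, socio-economic and clinical variables, and stratification variables) do not include time.

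The Study periods section gives five data collections: month 0, then after each of the three intervention periods, then month 24. The first group starts the intervention in month 1, the second in month 7 and the third in month 13, so month 0 is usual care for every dyad. The post-hoc sample size paragraph likewise works "with 3 intervention sequences, 5 periods, effect size of 7h/week, outcome variance of 400".

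**The concern.** A caregiver placed in the high-burden category by one measurement will, on average, score lower at the next one even if nothing has changed. Here that classifying measurement may also be the caregiver's first usual-care outcome, and most later records are intervention or follow-up. With no period term, model (1) can attribute the fall only to O. The low-burden category shows the mirror image.

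The resulting error has a predictable direction: LIVE would appear to help heavily burdened caregivers and to harm lightly burdened ones. A reader could easily take such a result as real effect modification. If the categories were instead set at later visits, the analysis would condition on the outcome after treatment had begun, which is a different problem and is not quantified here.

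**Working it through.** **Inputs from the SAP (Sample size estimation, Study periods).** The calculation "aimed to detect a difference of 7 h/week for the primary outcome RUD" and assumed that "the number of hours of informal care is 46 h/week with a standard deviation (SD) of 20 h/week". Variance is 400 (20²), with 3 sequences and 5 periods. The within-individual correlation is ρ = 0.1075, given for PADL.

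**Assumptions added here.** Month-0 median split on hours; normal outcome; compound symmetry, as model (1) implies; month 0 is in the model; equal sequences; no true effect and no secular trend. O stays 1 after crossover, as the Intervention effect table suggests, so the sequences are 01111, 00111 and 00011.

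**Step 1: the plan's own figure.** n per arm = 2(1.96 + 0.842)² × 20²/7² = 2 × 7.85 × 400/49 = 128.2, so 129 per arm and 258 in total. The t-based version gives 130 per arm, which is the stated 260. Then 260 × 1.2 = 312, rounded up to 315. So 7 and 20 h/week are the scale on which to judge the bias.

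**Step 2: regression to the mean.** The upper half at month 0 lies on average m = 20 × 0.798 = 15.96 h/week above the overall mean. At every later visit its expected excess is ρm. The fall is d = (1 − ρ)m = 0.8925 × 15.96 = 14.24 h/week, with no treatment effect.

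**Step 3: what model (1) makes of it (expected GLS estimate).** Let k be the number of treated visits: 4, 3 and 2 in the three sequences.
- Within-dyad sum of squares of O: Σ k(5 − k)/5 = 0.8 + 1.2 + 1.2 = 3.2.
- Between-dyad sum of squares: 5 × [(0.8 − 0.6)² + 0 + (0.4 − 0.6)²] = 0.4, with weight λ = (1 − ρ)/(1 + 4ρ).
- Within-dyad cross-product of O and outcome: −Σ kd/5 = −1.8d. The between-dyad cross-product is 0, because sequence is randomised.
- Spurious effect in the upper half: β₁ = −1.8d/(3.2 + 0.4λ).

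| ρ | d | λ | β₁ upper half (h/week) |
|---|---|---|---|
| 0.1075 | 14.24 | 0.624 | −7.43 |
| 0.3 | 11.17 | 0.318 | −6.04 |
| 0.5 | 7.98 | 0.167 | −4.40 |
| 0.7 | 4.79 | 0.079 | −2.67 |
| 0.8 | 3.19 | 0.048 | −1.78 |

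The lower half has the same values with a plus sign. At ρ = 0.1075 the bias is 7.43/20 = 0.37 SD.

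**Step 4: variants.**
- O = 1 only in the active period (k = 1 in each sequence): β₁ = −0.6d/2.4 = −0.25d, that is −3.56 at 0.1075 and −1.99 at 0.5.
- Post-baseline visits only: the expected profile is flat at ρm, so β₁ = 0 under compound symmetry.
- Period effects fitted within the category: they fit the profile (m, ρm, ρm, ρm, ρm) exactly, so β₁ = 0 at every ρ.
- Pooled treatment-by-burden interaction with shared period effects: the rise in one half cancels the fall in the other, the shared terms absorb nothing, and the high-minus-low difference is −14.86 at 0.1075, −8.79 at 0.5 and −3.57 at 0.8.
- Whole sample: m = 0, so this mechanism contributes nothing.

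**Step 5: simulation with 315 dyads, no true effect, mixed-model fits.** In 300 trials at ρ = 0.1075, model (1) per subgroup gave −7.3 and +7.4, significant in all. At 0.5 it gave −4.3 and +4.2, significant in 97–99%. With category-specific period effects the bias was −0.02 and +0.21, with 4–5% rejection. In a further 60 trials per correlation, the upper half gave −7.0 at 0.1075, and −1.8 at 0.8 with 75% falsely significant. Adding period effects within the upper half brought rejection to 5%, 5% and 10% at 0.1075, 0.5 and 0.8, compatible with 5% for 60 trials.

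**The case against.** The strongest reply is that the order of conditions does not itself cause bias. Sequences are randomised, so a separate fit within a burden category that includes period effects gives zero. That is right. A reader might infer that the usual-care-first layout is at fault, but the cause is a period term that is absent, or shared across categories. What remains is that the SAP writes no period term, and that adding a common one to a pooled interaction model would leave the bias in place.

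Second, neither month-0 classification nor month 0 as an analysed outcome is a stated rule. The Intervention effect table shows only four time points, with the first group already treated at the first of them, and the schedule lists baseline variables apart from outcome variables. If only the four post-baseline visits are analysed, the bias is zero under compound symmetry, though some returns if correlation decays over time. Five collection times and five periods are nevertheless in the text, so the problematic reading is open. The SAP does not rule it out.

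Third, the size depends on 0.1075, which is given only for PADL, one of three RUD categories. No correlation is given for the other two or for RSS. If RSS forms the categories and hours are the outcome, the bias shrinks with a cross-correlation that the SAP does not supply.

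Fourth, this is one of seven subgroup factors, and the SAP treats subgroup results as something to compare with the primary analysis. That limits the severity.

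**Conclusion.** The defect stands in a conditional form. The SAP forms a subgroup on its own primary outcome, leaves the classification undefined, and writes a model that cannot separate regression to the mean from treatment. With month-0 categories and month-0 records in the model, a null intervention would yield an apparent benefit in the upper half of about 7.4 h/week at correlation 0.1075, falling to 1.8 at 0.8, and an equal apparent harm in the lower half.

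A reader might infer that the plan will certainly report a spurious benefit as large as the 7 h/week target, or that the main result is compromised. The documents support neither. The first holds only at the PADL correlation, with the same instrument for category and outcome and O kept at 1 through follow-up. The second fails because the mechanism vanishes in the whole sample; what a secular trend would do to model (1) is a separate question. Severity: moderate.

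**What to change.** In Covariates and strata, state that burden category is fixed from the month-0 value, and name the instrument and the cut-points. State also which visits enter the model as outcome records. Estimate burden-subgroup effects with period effects specific to each category, either by separate fits with period fixed effects or by one model with treatment-by-category and period-by-category terms. Adding only common period effects to a pooled interaction is not enough. Merely dropping month 0 relies on compound symmetry.

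The change needs SAP wording and, in the single-model form with five periods, four extra period terms per additional category; no new data are required. The price is precision: in the simulation at the plan's SD and correlation, the standard deviation of the high-minus-low difference rose from about 1.8 to about 3.2 h/week. That wider interval is the correct one for this contrast.

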Primary objective	To determine treatment effect on caregiver burden measured as Resource Utilization Dementia (RUD), and the Relative Stress Scale (RSS). Based on the correlation coefficient, we will use all three subcategories of RUD separately. Total score will be used when assessing RSS. Further, we will evaluate the economic consequences of the treatment by calculating Incremental Cost-Effectiveness Ratio (ICER) and quality adjusted life years (QALY).
Secondary objectives	To determine treatment effect on quality of life (QoL) using the European Quality of Life – 5 dimension – 5 levels (EQ-5D-5L), EQ-5D-VAS scale, Quality of Life in Alzheimer's disease scale (QoL-AD); neuropsychiatric symptoms in dementia using the Neuropsychiatric Inventory 12 item (NPI-12), agitation in dementia using Cohen-Mansfield Agitation Inventory (CMAI), depression in old age (Geriatric Depression Scale - GDS), functional level for instrumental and personal activities (ADL and IADL), and the caregiver rating of clinical meaningful change using Clinical Global Impression of Change (CGIC).
Exploratory objectives	
In line with total score of RSS, we will also explore the treatment effect on both single and clustered items.
 
In line with total score of QoL based instruments (EQ-5D-5L, QoL-AD, QoL – CG, GDS), we will also explore the treatment effect on both single and clustered items
 
To assess the effect on pain in dementia using the Mobilization – Observation – Behavior – Intensity Dementia Pain Scale (MOBID-2)
 
To determine the characteristics of the dyads who had the highest improvement in RUD and RSS, i.e., those who benefitted the most from the intervention.

Endpoints	
Primary endpoint: Change in caregiver burden and informal care time among the caregivers in the intervention group during active intervention period, and the follow-up. Change in Cost-efficiency of treatment.
 
Secondary endpoint: Improvement in QoL for both PwD and caregivers. Reduction in neuropsychiatric symptoms in dementia and functional level during active intervention period and follow-up.
 
Exploratory endpoint: Reduction in pain during active intervention period.

Treatments	Allocation to municipal coordinator delivering the multicomponent LIVE intervention (L:learning, I: innovation, V: volunteering and E:empowerment) or care as usual.
Number of patients	315 dyads will be screened to achieve at least 105 dyads per municipality.

Safety analysis	Not applicable

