Efficacy: primary	x		
Efficacy: secondary	x		x
Efficacy: other	x	x	x

General Statistical Methods and Definitions

General statistical methods

The statistical analysis will be presented by treatment group for the different analysis sets as outlined in section 4.

Stepped wedge design (SWD) do not strictly feature a treatment and control group, and thus, the summary statistics will include all participants at baseline, and the characteristics according to intervention sequences.

Continuous variables will be summarized using descriptive statistics (means and interquartile ranges), and categorical variables will be presented by frequencies and percentages. A table will present the number of caregivers and PwD with the following data: missing values, mean, median, standard deviation and confidence intervals.

Means and median as well as percentages will be presented with 1 additional decimal place and standard deviation by 2 additional decimals.

If the number of PwD or caregivers in a category is 0, then percentage will not be displayed.

P-values will be reported to 3 decimal places.

Unless otherwise specified, all statistical tests will be two-sided.

Causal model

Due to the longitudinal structure of the collected trial data, we considered the following linear mixed model to estimate and identify the treatment effect due to the intervention. Our SWD, consisting of $j = 3$ municipalities and 3 steps, is a closed cohort design, and thus, time related confounders are important to adjust for [5] when assessing treatment effect.

Mixed-effects regression is one of the most common approaches when estimating the intervention effect in SWD [6, 7]. In our design, we will consider the following model as our primary analysis model, assuming a constant treatment effect.

$$(1) Y_{ijt} = \beta_0 + O_{ijt}\beta_1 + X_{ijt}\beta_2 + b_i + \epsilon_{ijt}$$

where notation Y_{ijt} refers to the primary outcome caregiver burden (RUD and RSS), elaborated in section 3 Study Design, for individual i nested in municipality j at time point t . O_{ijt} is the treatment indicator (effect of receiving assistance from a municipality coordinator) and β_1 is the average treatment effect parameter of interest. Since the study collects repeated observations from the same participants, we consider a longitudinal regression model that adjusts for participant-level random effect, $b_i \sim N(0, \sigma_b^2)$, which corresponds to a compound symmetric correlation structure.

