$\epsilon_{ijt} \sim N(0, \sigma_\epsilon^2)$ represents random error that changes across t and i .

X_{ijt} constitutes control variables which are demographic, socio-economic and clinical confounders (age, sex, caregiver marital status, work status, ADL function), and stratification variables used in the design stage.

Due to the non-normal distribution of hours and costs we will use both linear mixed-effects, as well as general lineal mixed regression model for assessing both primary variables. For RSS, and other continuous variables, we use Linear Mixed regression model. Log-transformation of the outcome will also be considered to address potential non-normality in the response.

Intervention effect

In secondary analysis, we will further examine the extent to which the treatment effect will depend on the calendar time when COVID lockdown happened, and the potential for delayed effect. We collectively refer these effects as heterogeneous treatment effect, and provide a schematic illustration following Section 3.2 of Li et al. (2020) [6]. The rationale is that there the lockdown during the pandemic may contribute to change in the intervention effect. In addition, the intervention may be most effective when it is first introduced, and the sustained effect may be smaller. Therefore, when modelling the intervention effect, we will allow for heterogeneous effect and assess the robustness of our primary analysis. The table below shows how the intervention effect can differ between periods (t) across different groups (g). The deltas (δ) constitute the intervention effect, and their subscript defines heterogeneous effects where δ_0 is the pre-lockdown intervention effect, δ_0^* is the intervention effect post-lockdown, and δ_1^* is the follow-up post-lockdown treatment effect.

When modelling the intervention effect, we will test the null-hypothesis (H_0)

$$\delta_0 = \delta_0^* = \delta_1^*$$

	$t = 1$	$t = 2$	$t = 3$	$t = 4$
$g = 3$			δ_0^*	δ_1^*
$g = 2$		δ_0^*	δ_1^*	δ_1^*
$g = 1$	δ_0	δ_1^*	δ_1^*	δ_1^*

Economic evaluation

If we identify an average treatment effect on one of the primary and secondary outcomes, we will use cost-efficiency (CEA) and cost-utility analysis (CUA) to evaluate the economic effects of the LIVE treatment.

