In cost-effectiveness analysis the effect is measured in health units (or other outcome measures depending on the context). The outcomes are common health measures in natural units, and the results are presented as cost per effect unit/outcome measure. In cost-utility analysis, also called cost per QALY analysis, the effect is measured as quality-adjusted life years (QALYs) on a scale of 0 (death) and 1 (full health). A quality-adjusted life year (QALY) captures both life years gained and improved health as a result of treatment [8, 9].

The economic evaluation will be measured at society level.

Costs and QALYs will be measured for each phase of 6 months

The cost-effective analysis will relate the difference in total mean costs at societal level per 6 months between all intervention -and usual care phases to the difference in RUD, RSS, QoLs, QALYs, NPI, function level such as ADL and IADL

The analysis will use a discounting rate at 3.5%.

Following other costs studies calculating RUD in an advanced economy setting, our analysis will use 35% of the Norwegian average income to value lost leisure time for retired caregiver.

The primary economic evaluation will use the opportunity cost method to assess the costs of informal caregiving. For a sensitivity analysis, the replacement cost will be used.

Unit costs will be based on information from Statistics Norway and information from the primary health care institutions in each municipalities.

Covariates and strata

In the main statistical analyses, the following covariates are used for both caregivers and PwD.

For PwD: Age, sex, marital status, cohabitation status, number of co-caregivers, clinical characteristics of dementia (dementia etiology, neuropsychiatric symptoms, functional level)

For Caregivers: Age, sex, marital status, cohabitation status, numbers of co-caregivers involved in caregiving for the PwD, work status, use of health care services,

Groups, municipalities

Municipalities will be grouped in the main analysis and used as an adjustment variable (fixed effects). This is not the case for district municipalities as we consider that the dyads are similar within municipalities

Subgroups

In subgroup analyses, the following covariates will be used to define relevant subgroups:

- Gender (male, female)
- Work (retired and working caregivers)
- Caregiver relation (spouse, children)
- Residency (living alone, or with caregiver)

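### The SAP names two different primary tests, leaves calendar period out of the primary model, and gives no rule for success across its primary variables

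*SAP*

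**What the plan says.** **Primary model.** The Causal model section introduces equation (1) with "we will consider the following model as our primary analysis model" and calls β₁, the average treatment effect on RUD and RSS, the parameter of interest. The equation has an intercept, a treatment indicator, control variables X, a participant random effect and error. Just before it, the SAP says that "time related confounders are important to adjust for". X is then said to hold "demographic, socio-economic and clinical confounders (age, sex, caregiver marital status, work status, ADL function), and stratification variables used in the design stage". The Covariates and strata section opens with "In the main statistical analyses, the following covariates are used for both caregivers and PwD" and gives further lists, with municipality as a fixed effect. None of these lists contains period or calendar time.

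**Primary test.** The Primary efficacy analysis section states H0 and H1 and then says "LIVE treatment denotes the proportion of caregivers experiencing improvement in care burden. The primary hypothesis will be statistically assessed by means of a" chi-square test at one-sided 2.5%, which it equates with two-sided 5%. Lower hours and lower RSS count as better. No cut-off, instrument or reference visit is given.

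**Primary variables.** The same section says "The primary efficacy analysis variable caregiver burden is based on two variables", followed by "The first is RUD, divided in three categories: number of hours the last 30 days invested in personal, instrumental and supervisory care"; RSS is the other variable. The primary objective in the Study Design table says "Based on the correlation coefficient, we will use all three subcategories of RUD separately", with the RSS total. For hours, the Causal model section keeps two model types and leaves a log-transformation open.

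**The concern.** A difference in mean hours estimated by a mixed model and a difference in the proportion of caregivers who improve are different quantities with different tests. The same data can be positive on one and negative on the other, and the SAP does not say which result counts. The proportion cannot be computed from the text either: every caregiver is seen under both conditions, and nothing says how such a person enters a two-group table.

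The missing period term matters because in a stepped wedge the treated share rises with calendar time by design, and this trial ran through a lockdown. Without the term, falling hours look like benefit, and rising hours hide benefit or look like harm.

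Without a success rule, the team could decide after seeing results whether one positive variable out of four is enough.

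**Working it through.** **1. The plan's own sample size.** The Sample size estimation section gives a difference of 7 h/week, SD 20, 80% power and 5% significance. Per group: 2 × 20² × (1.960 + 0.842)² / 7² = 128.1, so 129 per group and 258 in total, against the stated 260. The trial was sized for one comparison of means, not of proportions.

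For contrast, take improved to mean any fall from baseline (an assumption), with the SAP's within-person correlation ρ = 0.1075. The SD of a change is √(2 × 400 × 0.8925) = 26.7. A 7 h/week effect then becomes 50.0% against Φ(7/26.7) = 60.3%. A single two-group comparison of these proportions needs about 726 dyads for 80% power; 260 dyads give 39%.

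**2. Model (1) with and without period.** From the SAP: SD 20, five visits, three sequences, ρ = 0.1075, and 315 × 0.80 = 252 dyads, so 84 per sequence. Assumed: ρ = 0.5 as an alternative, a linear drift of 1 or 2 h/week per period, treatment on schedule, follow-up visits counted as treated, and no covariates.

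Each person's covariance is V = 400[(1−ρ)I + ρJ]. The standard error (SE) comes from (Σ D′V⁻¹D)⁻¹, and the bias from applying the estimator to the drift alone. Two-sided rejection is Φ(bias/SE − 1.96) + Φ(−bias/SE − 1.96). At ρ = 0.1075 and drift 1, for example, 2.32/1.110 = 2.09, and Φ(0.13) = 0.55.

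| No true effect | ρ = 0.1075 | ρ = 0.5 |
|---|---|---|
| No period term: SE | 1.110 | 0.854 |
| Bias, drift 1 / 2 | 2.32 / 4.64 | 2.45 / 4.90 |
| Rejection, drift 1 / 2 | 55% / 99% | 82% / 100% |
| Period fixed effects: SE | 1.895 | 1.543 |
| Bias; rejection | 0; 5% | 0; 5% |

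With a true benefit of 7 h/week and hours rising 2 per period, the model without period is expected to show only 7 − 4.64 = 2.36 (ρ = 0.1075) or 7 − 4.90 = 2.10 (ρ = 0.5). With period effects, power is Φ(7/1.895 − 1.96) = 96%, or Φ(7/1.543 − 1.96) = 99.5%.

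**3. The chi-square test.** Same setting, any fall from baseline counted as improved, 6,000 simulated trials per case. Two readings: all post-baseline visits pooled, or the first post-baseline visit only.

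| | ρ = 0.1075 | ρ = 0.5 |
|---|---|---|
| No effect, pooled, no drift | 4% | 5% |
| No effect, pooled, drift 1 to 2 | 9% to 24% | 13% to 39% |
| No effect, first visit | 5% to 6% | 5% to 6% |
| True 7 h/week, pooled, no drift | 82% | 97% |
| True 7 h/week, pooled, hours rising 1 / 2 | 61% / 36% | 85% / 57% |
| True 7 h/week, first visit | about 36% | about 55% |

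With a true 7 h/week effect, period-adjusted β₁ and the pooled chi-square disagree on the same data in 18% (ρ = 0.1075) or 3% (ρ = 0.5) of trials without drift. With rising hours they disagree in 37% to 61% or 14% to 43%. Against the first-visit chi-square the figures are 61% to 62% or 44% to 46%.

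**4. Multiplicity, if any single success counted.** Four independent tests at one-sided 2.5% give 1 − 0.975⁴ = 9.6%; at a correlation of 0.7 (assumed) this is 6.5%. Two tests give 1 − 0.975² = 4.9%, or 4.2% at 0.7. The SAP gives no effect size for RSS or for the RUD categories other than PADL, so power under an all-must-succeed rule cannot be stated.

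**The case against.** - **Coding of follow-up.** The bias in step 2 depends on follow-up visits being coded as treated. The treatment indicator is described as receiving help from a coordinator, and each group's intervention lasts six months. If only the visit that ends the active period is coded as treated, a linear drift gives no bias and rejection stays at 5%. This is correct. But the primary endpoint includes follow-up, and the Intervention effect table gives follow-up its own treatment effects. The cancellation also needs a straight trend. Under this coding the bias is (5/4) × (mean shift at visits 1 to 3 − mean shift over all five visits). A shift of 2 h/week at visits 1 to 3 only gives (5/4) × (2 − 6/5) = 1.0 h/week.
- **Intent.** The SAP says time should be adjusted for, so an analyst might add period unprompted. The intent is there, but the equation and the enumerated covariates do not carry it out.
- **The chi-square readings are constructed.** The SAP does not say pooled, and the first-visit version holds its error level. Both points stand: the first-visit version is valid but weak, and having to invent a reading is part of the defect. The disagreement rates also use β₁ with period added, so they illustrate the conflict and do not measure the text as written.
- **Sidedness.** The rejection rates in steps 2 and 3 are two-sided. Under the one-sided rule, false benefit arises only if hours fall; if they rise, the harm is lost power. No document gives the size or direction of drift.
- **Power.** The SAP's post-hoc calculation asks for 240 dyads, and that figure could not be reproduced. The 96% assumes the SAP's SD and ρ and treatment on schedule, which Covid-19 disrupted.

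**Conclusion.** The concern holds and must be fixed. The conflict between β₁ and a chi-square test on an undefined proportion is plain in the text and needs no assumption. So are the absence of a period term from model (1) and its covariate lists, and the absence of a success rule for three RUD categories and RSS.

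The size of the period problem does rest on assumptions. With follow-up counted as treated and a linear drift of 1 to 2 h/week per period, the bias is a third to over two thirds of the 7 h/week target (2.32/7 = 33%; 4.90/7 = 70%). With active-period coding it disappears for a straight trend but not for an uneven one. The multiplicity figure applies only if one success were enough, which the SAP neither permits nor rules out.

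**What to change.** Before the outcome data are analysed:

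1. In the Primary efficacy analysis section, make the test of β₁ = 0 at two-sided 5% the decision rule; the SAP already treats this as equivalent to one-sided 2.5%. Delete the chi-square test and the proportion, or keep them as supportive with cut-off, instrument, reference visit and compared periods defined.
2. Write period fixed effects into equation (1) and the covariate lists, and state how follow-up visits are coded in the treatment indicator.
3. Name one model for RUD hours as primary. List the other model and any log-transformation as sensitivity analyses, saying which outcomes they cover.
4. State one success rule: one named primary variable, a fixed testing order, or Holm over the three RUD categories and the RSS total. Say also where cost-efficiency belongs, since the Study Design table lists it under the primary endpoint and the efficacy section makes it the secondary hypothesis.

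This is SAP wording and needs no new data. Period effects raise the SE of β₁ from about 1.1 to 1.9 h/week (ρ = 0.1075), leaving 96% power. Holm's first step over four variables uses two-sided 0.0125 (critical value 2.498), so power becomes Φ(7/1.895 − 2.498) = 88%, or 98% at ρ = 0.5. One named primary gives up confirmatory claims on the others; a fixed order tests later variables only if earlier ones succeed.
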